### 4.1 Participant Inclusion and Exclusion Criteria

#### 4.1.1 Inclusion criteria

Participants must meet all of the inclusion criteria to enter into the study.

The entry inclusion criteria are:

- 1. Age 18-54
- 2. Lives in or near Atlanta metropolitan statistical area (MSA)
- 3. Plans to be in Atlanta for the majority of the 12 weeks of enrollment
- 4. Able to independently complete survey instruments in English
- 5. Male sex at birth
- 6. Currently identifies as male
- 7. For MSM, self-report to have only had sex with men in the past four weeks
- 8. For MSW, self-report to have only had sex with women in the past four weeks
- 9. Self-report no transgender sex partners in the past four weeks
- 10. Self-report at least 1 anal (MSM) or vaginal (MSW) sex act in the past four weeks
- 11. For MSM, self-report intends to have sex only with men in the next 12 weeks
- 12. For MSW, self-report intends to have sex only with women in the next 12 weeks
- 13. For MSM, self-reports an insertive role in the past four weeks or willing to be the insertive partner when using study condoms for anal sex
- 14. Willing and able to have sex using a latex condom provided by study
- 15. For MSW, report that current partner is not currently pregnant
- 16. For MSW, report that current partner does not desire to become pregnant currently or in the next 12 weeks
- 17. Consistently able to maintain an erection while using condoms
- 18. Not allergic to latex
- 19. Current partner(s) not allergic to latex
- 20. No genital piercings
- 21. For MSW, female current partner(s) does (do) not have vaginal piercings
- 22. For MSM, male current partner(s) does (do) not have anal piercings
- 23. Current partner(s) not known to be HIV-positive
- 24. Self-report absence of sexually transmitted infections, including HIV
- 25. Negative HIV rapid test result or confirmed negative HIV test at baseline
- 26. Willing to provide at least two means of contact
- 27. Willing to only use lubricant provided by study
- 28. Not allergic to water-based lubricant
- 29. Current partner(s) not allergic to water-based lubricant
- 30. Willing to use a fitting tool to determine penile dimensions

All participants must provide written informed consent to participate in the study.

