Research is also needed to better understand condom performance for anal sex applications. MSM are estimated to account for nearly two out of every three new HIV infections in the United States,  and are the only group with increasing HIV incidence.  Previous estimates of clinical condom failure (slippage or breakage) during anal sex have often not measured failure at the event level. Two studies have assessed clinical condom failure prospectively at the event level, with clinical failure reported in 6.3%  and 6.9%  of anal sex acts. One study found that fitted condoms had lower breakage failure rates than standard condoms for anal sex. 

For this study, we will use a mobile-optimized, web-based home daily coital log that allows for event level measurement. We anticipate that use of this system will decrease recall bias, avoiding possible limitations of paper-based recall systems that do not have time stamping to accurately determine the time of form completion. We anticipate that, with the use of a system that decreases recall bias, we may have higher sensitivity to detect clinical failure across all study conditions (fitted, thin and standard).

For purposes of this study, a "standard" condom is defined by dimensions commonly sourced by the United Nations Population Fund (UNFPA) and United States Agency for International Development (USAID), which procures the majority of the world's condoms ([name], BS, email communication, June 23, 2015). These dimensions are 185mm ± 10mm length, 53mm

 $\pm$  2mm width, and 70 microns  $\pm$  10 microns thick ([name], BS, email communication, June 23, 2015). "Thin" condoms for this study will be of identical width and length to "standard", but 50 microns  $\pm$  5 microns thick. Fitted condoms will be produced in a range of sizes (uploaded to eIRB) with thickness of 70 microns  $\pm$  10 microns, with a participant's fitted size as determined by their use of a fitting system consisting of a paper template graduated with non-sequential numbering and lettering (uploaded to eIRB). All condoms will be manufactured by Karex International. Condoms will be manufactured using the same latex formulation and silicone lubricants (approximately 400mg per condom), and with similar parallel wall designs.

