#### 3. STUDY OVERVIEW

# 3.0 Study Design

This study is a randomized crossover trial of 252 HIV-negative MSM and 252 HIV-negative MSW. Every participant in the trial will receive a batch of five fitted condoms, a batch of five thin condoms, and a batch of five standard condoms over a series of study visits. We will randomize the order in which fitted, thin, and standard condoms will be distributed. Eventlevel data based on a home coital log will be collected regarding pleasure and total clinical failure (Aims 1, 3 and 4), and data regarding overall condom preference (Aim 2) will be collected at the final study visit. All participants will complete an informed consent form (ICF) (uploaded to eIRB). Eligibility assessment will include HIV testing and symptomatic STI and acute HIV screening. The order in which study condoms will be received will be determined by permuted block randomization. Participants will be provided access to a mobile-optimized, web-based home coital log diary that is 21 U.S. Code of Federal Regulations (CFR) Part 11 compliant, in which participants will document each instance of study condom use as soon as possible following any vaginal or anal sex acts. Log entries will include assessment of pleasure and clinical failure, as well as other pertinent information such as substance use, lubricant, and any potential events including errors during application. Participants will be enrolled over a period of approximately 6-12 months, depending on the speed of recruitment. Each participant will be followed for six to twelve weeks after enrollment, depending on their use of study condoms in each two-week period between study visits (Figure 1). Participants will return for a follow-up visit two weeks after baseline. Participants will be given up to four weeks to use each study condom set; after 4 weeks with a set of condoms, participants will be automatically crossed over into the next study condition. If all condoms are used within the first two weeks, participants will crossover to the next randomized study condoms at that point (Figure 1). If participants do not use all study condoms in the first two weeks after the have been dispensed, participants will be given a second 2-week period to use the batch of condoms. Throughout the duration of study participation, coital logs will be completed.

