#### 4.1.2 Exclusion criteria

Potential participants meeting any of the exclusion criteria at baseline will be excluded from participating in the study.

The exclusion criteria for the study are:

- 1. <18 years of age or >54 years of age
- 2. Does not live in or near Atlanta MSA
- 3. Does not plan to be in Atlanta for the majority of the 12 weeks of enrollment
- 4. Unable to independently complete survey instruments in English
- 5. Not male sex at birth
- 6. Does not currently identify as male
- 7. Self-report to have had sex with both men and women in the past four weeks
- 8. Self-report transgender sex partners in the past four weeks
- 9. Self-report no anal (MSM) or vaginal (MSW) sex act in the past four weeks
- 10. Self-report intends to have sex with both men and women in the next 12 weeks
- 11. Never the insertive partner for anal sex or not willing to be the insertive partner when using study condoms for anal sex
- 12. Not willing or unable to have sex using a latex condom provided by study
- 13. Plans to not have sex in the next four weeks
- 14. For MSW, report that current partner is currently pregnant
- 15. For MSW, report that current partner desires to become pregnant currently or in the next 12 weeks
- 16. Unable to consistently maintain an erection while using condoms
- 17. Allergic to latex
- 18. Current partner(s) allergic to latex
- 19. Genital piercings
- 20. For MSW, female current partner(s) has (have) vaginal piercings
- 21. For MSM, male current partner(s) has (have) anal piercings
- 22. Current partner(s) known to be HIV-positive
- 23. Self-report presence of sexually transmitted infections, including HIV
- 24. Confirmed HIV positive at baseline
- 25. Not willing to provide at least two means of contact
- 26. Not willing to only use lubricant provided by study
- 27. Allergic to water-based lubricant
- 28. Current partner(s) allergic to water-based lubricant
- 29. Not willing to use a fitting tool to determine penile dimensions

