#### 5.3 Lubricant

Study staff will provide participants with two packets per condom of 10ml commercially available condom-compatible water-based lubricants. Participants will be instructed not to use any other lubricants when using study condoms. MSM will be instructed to use lubricant with all anal sex acts. Coital log entries indicating incorrect use of lubricant will be excluded from clinical failure analyses (Aims 3 and 4). This includes use of non-study lubricant, use of lubricant inside the condom, and absence of lubricant use for anal sex.

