# 10.2 Risks to participants

Following are anticipated risks to participation, and procedures to reduce risk:

Persons may learn they have HIV or possibly an STI, and this may be upsetting.

To minimize this risk, we will have counselors and other study staff who have been trained in HIV counseling and testing conducting HIV testing and providing referrals to participants. Referrals for HIV treatment and care and STI testing and treatment will be made to providers familiar with MSM-specific health issues.

• Persons may be uncomfortable with some survey questions.

To minimize this risk, we will be very clear during the consent process regarding the types of data that we will collect, and we will make optional questions not pertinent to key study outcomes. Participants who find the surveys to be generally uncomfortable can choose to discontinue participation in the study.

• Persons may have their study information compromised.

Procedures for data security are described in section 10.6. All study staff will sign a confidentiality agreement (uploaded to eIRB).

• Persons who have blood drawn for confirmatory HIV testing may have discomfort, bruising, or a local infection at the site of venipuncture.

This is a typical risk of having blood drawn in any setting. The study phlebotomists will be certified and experienced in phlebotomy, as described in section 7.4, to minimize this risk.

• Persons using study condoms may experience condom failure.

Condom failure is a risk in any condom clinical trial. However, the condoms in this trial have all been cleared by the FDA. To minimize risk of condom failure, participants will be instructed in proper condom use and asked to report any issues with study condoms.

• Persons using study condoms and lubricant may experience reactions or side effects.

Reactions and side effects are a risk with any condom or lubricant use. Participants with known allergies to latex or water-based lubricant will be excluded from the study. Participants with reactions or side effects to study products may be study stopped.

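### The allergy criteria name latex and water-based lubricant but not the silicone lubricant on every study condom, so a man or partner known to react to it passes every allergy item.

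*Protocol*

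**What the plan says.** Section 1 of the protocol defines the three condom types and states that all come from one manufacturer, "using the same latex formulation and silicone lubricants (approximately 400mg per condom". Section 3.0 gives each participant "a batch of five fitted condoms, a batch of five thin condoms, and a batch of five standard condoms".

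The water-based product is a different item. Section 5.3 has staff supply "two packets per condom of 10ml commercially available condom-compatible water-based lubricants". Section 7.1.2.5 tells MSM to use it for every anal sex act and leaves its use to need for MSW.

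The allergy criteria are written component by component, for the man and for his current partner(s):

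- Latex: inclusion 18 ("Not allergic to latex") and 19, mirrored by exclusion 17 and 18.
- Water-based lubricant: inclusion 28 ("Not allergic to water-based lubricant") and 29, mirrored by exclusion 27 and 28 ("Current partner(s) allergic to water-based lubricant").

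Section 10.2, describing how the risk of reactions to the products is reduced, says: "Participants with known allergies to latex or water-based lubricant will be excluded from the study".

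**The concern.** The protocol screens known allergies by naming the materials that the man and his partner will contact. It describes three such materials: the latex, the silicone lubricant on the condom, and the water-based lubricant in packets. The criteria name the first and the third. The second is on every condom in every condition. MSW may leave the packet product unused, yet it is screened for. Nobody who uses a study condom can avoid the condom's own lubricant, yet it is not.

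The main stake is safety, particularly for partners. They are exposed, section 10.1 describes consent by participants only, and the follow-up questions in section 7.1.3.4 ask about the participant's own discomfort and, for partners, only about pregnancy. Entry screening is therefore the main written protection that a partner has against a reaction that is already known.

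A lesser stake is avoidable loss. Crossing over to the next condition brings no relief from a material common to all three, so an affected man could be paused or stopped (section 4.4) and contribute little to the within-man comparisons.

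**Working it through.** The check is a comparison of sections. The point rests on no power, alpha or event-rate figure.

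**Step 1: which materials are present, and which are screened.**

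| Material | Where described | Exposure | Allergy criterion, man | Allergy criterion, partner |
|---|---|---|---|---|
| Latex | Section 1 | Every condom | Inclusion 18, exclusion 17 | Inclusion 19, exclusion 18 |
| Silicone lubricant, about 400 mg | Section 1 | Every condom | None | None |
| Water-based lubricant in packets | Section 5.3 | Every act for MSM; if needed for MSW | Inclusion 28, exclusion 27 | Inclusion 29, exclusion 28 |

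Section 10.2 lists the first and third rows only. Sections 5.0 to 5.3, which describe the products, do not mention the silicone lubricant, so staff working from them would see only the water-based product.

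**Step 2: how many condoms carry it.** Three conditions × 5 condoms = 15 per man, all of them silicone-lubricated.

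**Step 3: whether another entry rule closes the gap.** The nearest is inclusion 14, with exclusion 12 as its mirror, which requires the man to be able and willing to use the latex condoms that the study supplies. A man who knows that he reacts to the condom's lubricant might rule himself out here. The rule does not ask about allergy or about the lubricant, and it applies to the participant alone. No other criterion asks about a partner's tolerance of the condom beyond latex.

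**Step 4: whether later safeguards close it.** Section 4.4 pauses a man with condom or lubricant problems until the study physician has assessed them, section 7.1.3.4 asks about discomfort at each follow-up visit, and section 7.2.5 adds an independent physician. All of these begin after the reaction has happened.

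**Step 5: exposure before the first scheduled check.** Section 7.1.2.6 issues one batch of five at a time, and the first follow-up visit is planned at two weeks. The most that can be used before that visit is 5 × 400 mg = 2,000 mg, about 2 g. Using all three batches would give 15 × 400 mg = 6,000 mg, about 6 g, but that total describes a man who completes the study without being paused. It is not the relevant figure for someone who reacts.

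**Step 6: number affected.** No section gives a frequency of known reactions to silicone lubricant, so no estimate follows from the documents. The 20% in section 6.2 is the expected rate of any discomfort or other issue with condoms or lubricant. It does not measure known silicone reactions.

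**The case against.** The best case against the point has four parts.

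First, the criteria and section 10.2 agree with each other: both name two allergens, and the criteria implement exactly those two. No passage promises to exclude everyone who reacts to any component. That stands. This is an incomplete list set against the product description, not a conflict between two rules.

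Second, nothing in the documents shows that silicone condom lubricant is a hazard, that people would know they react to it, or how often this happens. Section 10.2 adds that all the condoms are FDA-cleared. This stands as a limit on size. A reader might infer a count by assuming a frequency: 0.2% to 1% of 504 enrolled men gives 504 × 0.002 = 1.0 to 504 × 0.01 = 5.0. The documents do not support that range, and the result only restates the assumption.

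Third, inclusion 14 and the monitoring offer some protection. This stands in part. The first may catch some participants, and the second limits exposure once a reaction is reported. Neither identifies a partner with a known reaction before exposure.

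Fourth, the screening form is an upload to the ethics board's system and was not available, and the consent pages were removed. Either might already ask about the condom's lubricant. That cannot be ruled out. The written criteria and section 10.2 do not ask.

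**Conclusion.** The point holds as a minor one. Read literally, the allergy criteria admit a man who is known to react to the lubricant on all 15 of his condoms, or a man whose current partner is. Inclusion 14 may informally stop some of the former and does not cover the latter. Post-enrolment safeguards limit harm without preventing the first exposure.

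The number affected cannot be estimated from the documents. The conclusion assumes that the screening form follows the written criteria and asks nothing more.

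A reader might go further and infer damage to the trial's comparisons. The documents do not support that. Section 1 gives all three condom types the same lubricant, so there is no reason to expect bias in fitted versus standard for pleasure, preference or clinical failure. Any loss of men from this cause would add to the 20% that section 9.3 already plans for, and that section allows further recruitment if loss is greater.

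**What to change.** Reconcile sections 4.1.1, 4.1.2 and 10.2 with the product description in section 1, so that the known-allergy screen for participant and partner covers the lubricant on the study condoms as well as the packet lubricant. In practice:

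- extend inclusion 28 and 29 and exclusion 27 and 28 to name both lubricants;
- make the same change to the risk paragraph in section 10.2;
- check that the screening eCRF asks the matching question for man and partner. If it already does, only the protocol text needs to change.

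The cost is new wording in four criteria and one paragraph, possibly one screening item, and the ethics-board submission that section 12.2 requires for any protocol change. The downside is at most a few extra screen failures. Sample size and analysis are unaffected.

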#### 4.1.2 Exclusion criteria

Potential participants meeting any of the exclusion criteria at baseline will be excluded from participating in the study.

The exclusion criteria for the study are:

- 1. <18 years of age or >54 years of age
- 2. Does not live in or near Atlanta MSA
- 3. Does not plan to be in Atlanta for the majority of the 12 weeks of enrollment
- 4. Unable to independently complete survey instruments in English
- 5. Not male sex at birth
- 6. Does not currently identify as male
- 7. Self-report to have had sex with both men and women in the past four weeks
- 8. Self-report transgender sex partners in the past four weeks
- 9. Self-report no anal (MSM) or vaginal (MSW) sex act in the past four weeks
- 10. Self-report intends to have sex with both men and women in the next 12 weeks
- 11. Never the insertive partner for anal sex or not willing to be the insertive partner when using study condoms for anal sex
- 12. Not willing or unable to have sex using a latex condom provided by study
- 13. Plans to not have sex in the next four weeks
- 14. For MSW, report that current partner is currently pregnant
- 15. For MSW, report that current partner desires to become pregnant currently or in the next 12 weeks
- 16. Unable to consistently maintain an erection while using condoms
- 17. Allergic to latex
- 18. Current partner(s) allergic to latex
- 19. Genital piercings
- 20. For MSW, female current partner(s) has (have) vaginal piercings
- 21. For MSM, male current partner(s) has (have) anal piercings
- 22. Current partner(s) known to be HIV-positive
- 23. Self-report presence of sexually transmitted infections, including HIV
- 24. Confirmed HIV positive at baseline
- 25. Not willing to provide at least two means of contact
- 26. Not willing to only use lubricant provided by study
- 27. Allergic to water-based lubricant
- 28. Current partner(s) allergic to water-based lubricant
- 29. Not willing to use a fitting tool to determine penile dimensions

#### 4.2 Recruitment Procedures

# 4.2.1 Primary recruitment method

The primary method of recruitment for both MSM and MSW will be venue-based, face-to-face recruitment that will take place in a variety of public and private venues in Atlanta where men congregate. These will include bars, dance clubs, retail stores, street corners, restaurants, churches, college campuses, and other public places.

### 4.2.1.1 Primary recruitment procedures

All recruiters will be trained in the Collaborative Institutional Training Initiative (CITI)'s ethical conduct of research. At the recruitment event, trained recruiters will approach potential participants, obtain permission to screen, and administer

a brief recruitment script and set of screening questions using a handheld device (recruitment materials uploaded to eIRB).

Eligibility will be assessed in three stages, because of the detail and sensitivity of some of the eligibility criteria. The first stage will be during this recruitment event, where we will screen on a subset of the eligibility criteria, such as age and recent sexual activity. Potential participants meeting these criteria will be asked to provide first name, first, middle (if applicable), and last initial and contact info (email address and phone numbers).

Recruiters will hand out study contact cards and commercially-available condoms (not fitted) and lubricant to eligible or interested participants. We will provide commercially-available (not fitted) condoms and lubricant to all participants, regardless of their participation in the screener or their study eligibility.

Every potential participant providing this contact information will be sent an electronic consent form that will indicate willingness to receive a full eligibility screening. Potential participants affirmatively completing this electronic consent will be contacted and screened for the full list of eligibility criteria. Those who indicate they are not willing to consent will not be contacted, and their information will be deleted from the recruitment database. Those determined to pass the second stage of eligibility criteria will be mailed or emailed a fitting tool and scheduled for a study visit (which will include a further consent process, detailed below).

Potential participants providing contact information but who have not completed the electronic consent process will be contacted via phone to assess their interest in the study. These participants will be given the option of completing a verbal consent process for eligibility screening over the phone. Potential participants who complete the verbal consent process will be screened for the second stage of eligibility criteria, and those eligible will be scheduled for a study visit. We have uploaded to eIRB versions of the verbal and electronic screening consent.

Eligible participants will be given the option to determine their fitted condom size prior to attending their baseline visit, using the fitting tool sent following the phone screening and an electronic demonstration video.

Scheduling and phone scripts are described in more detail in section 7.1.1 and are uploaded to eIRB.

